## 4.2 Intervention/Treatment procedures (by visits)

There will be two intervention/treatment visits, both occurring on POD#1. On POD#1 in the morning, patients in both groups will be visited by the research assistant. Patients in the VR arm will be offered the VR device for up to 30 minutes. Patients in the control arm will be offered an iPad for up to 30 minutes. After a total of 30 minutes maximum, the session will end. Routine data will be collected on pain scores and PCA use as above for both groups. On POD #1 in the afternoon, a research assistant will return for patients in both groups. For participants in the intervention group, this VR session will be again offered for up to 30 minutes. Patients in the control arm will be offered an iPad for up to 30 minutes. If a patient declines to participate, the reason for declining will be asked for and recorded.

To evaluate efficacy, the following will be recorded:

- Primary outcomes:
  - Postoperative pain scores
  - Postoperative PCA opioid use surrounding intervention (morphine equivalents)
- Secondary outcomes:
  - Patient and caregiver satisfaction scores
  - Presence of dizziness/nausea
  - Time of discontinuation of VR if less than 30 minutes

## 4.3 Follow-up procedures (by visits)

There will be a follow-up survey using the PHBQ-AS form to assess new onset behavior change at approximately 48-72 hours postop and 7-10 days postop via a phone call from a member of the research team. These scores will be recorded and analyzed between both study groups.

#### 4.4 Unscheduled visits

Not applicable

#### 4.5 Concomitant Medication documentation

PCA opioid use surrounding intervention (morphine equivalents), at time intervals as detailed above, will be recorded. Any anti-nausea medication requested during the intervention will be recorded. Given that our study will take place on POD#1, perioperative medications given intra-operatively will not be included for analysis.

#### 4.6 Rescue medication administration

Addressed in section 4.5

## 4.7 Subject Completion/ Withdrawal procedures

Patients and/or caregivers can withdraw from the study at any time for any reason, and this will be documented. Standard of care practices will not be influenced by inclusion, exclusion or withdrawal from the study. If patients are excluded from the study at any point, the reason(s) will be noted, and every effort will be made to replace that patient with another subject within the same subgroup. The goal is to have 10 patients in each arm complete the study. Study duration will be up to 13 days for each patient and will conclude following the second postoperative telephone survey or after postoperative day 13, whichever comes first.

#### 4.8 Screen failure procedures

Patients that fail to be screened and considered for the study will not be included.

## 5 STUDY EVALUATIONS AND MEASUREMENTS

- Variables that will be abstracted from the medical charts:
  - Name, medical record number, phone number
  - Age (years), gender (male or female), race or ethnicity, weight (kg), BMI (kg/m2), heart rate (0-200 beats/min), and blood pressure (0-250/0-150 mmHg) pre-operatively
  - Surgery type, current medications
  - Pain scores, vital signs
  - Intraoperative record
- o Baseline evaluation will include chart review, by phone or in person assessment for inclusion and exclusion criteria, vital sign assessment, study consent and orientation.
- Preoperatively, baseline vital signs will be obtained and recorded by nursing staff per UNC standard of care practices. Additionally, two pain scores will be assessed: FACES by the patient and FLACC by the research assistant.
- O Postoperatively, pain scores including FACES scale by the patient and FLACC scores by the research assistant will be recorded immediately prior to intervention (T=0) and at end of intervention (T=30); FLACC score will also be recorded at the 10 minute mark (T=10). PCA use, in mcg or mg as appropriate, for the hour prior to intervention (T=-60-0), during intervention (T=0-30), and one hour after intervention is complete (T=30-90) will be recorded. Total number of minutes of electronic device use will be recorded. This data will be recorded by the research assistant.
- o PCA use will be converted to morphine equivalents at time of data entry.

Descriptions of each questionnaire and scale, including total score computations:

Short State-Trait Anxiety Inventory (STAI) – 6 statements (i.e., 'I feel calm', with 1=Not at all, 2=Somewhat, 3=Moderately, 4=Very much). Scores 6-24, with 6 signifying no anxiety and 24 points signifying the highest level of anxiety. This short form of the STAI was used and validated in children aged 5-16 years (Schisler et al, 1998; Apell et al, 2011)

FACES (Wong-Baker) Pain Rating Scale – Self-assessment scale; patients select a face that illustrates the pain they are experiencing. Scores 0-10, with 0=No hurt and 10=Hurts worst (wongbakerfaces.org)

FLACC (Face, Legs, Activity, Cry, Consolability) – Observer assessment scale, with 5 categories (i.e., 'Face', with 0=No particular expression or smile, 1=Occasional grimace or frown, 2=Frequent to constant quivering chin, clenched jaw). Scores 0-2 in each category, for total scores 0-10, with 0=No observed pain and 10=Most observed pain

PHBQ-AS (Post Hospitalization Behavior Questionnaire for Ambulatory Surgery) – 11 items on a five-point scale (i.e., 1=Much less than before, 5=Much more than before). Total scores 11-55 (Jenkins et al, 2015)

These are all validated scoring systems in pediatric populations.

We will utilize the short STAI, as above.

Units of measurement for all variables of interest: Questionnaires and scales as above. In addition, hours since anesthesia end to start of visit (hours), PCA use (mcg or mg, at T=-60-0, 0-30, 30-90 min; converted to morphine equivalents at time of data entry), patient declines (0=Yes, 1=No), total duration of electronic device use (min), presence of dizziness (0=No, 1=Yes), presence of nausea (0=No, 1=Yes), anti-nausea medication requested during intervention (0=No, 1=Yes).

Patient and caregiver satisfaction: Qualitative satisfaction will be documented, divided into positive and negative comments.

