In the VR arm, VR devices will be used with pre-selected virtual reality program options. In the control arm, patients will be offered an iPad preloaded with a variety of games. Both groups of participants will also receive the postoperative standard of care including a PCA for pain control.

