## 1.3 Non-Clinical and Clinical Study Findings

By exploring non-pharmacologic methods of postoperative pain management in the form of virtual reality distraction, we hope to contribute to effective means of management for the common condition of postoperative pain. Postoperative risks associated with children are related to opioid administration and include over-sedation, respiratory depression, nausea and vomiting, and increased PACU stay. By providing a non-pharmacologic distraction method, we plan to minimize postoperative pain, opioid requirements, and lessen their possible adverse effects. As a result, children may receive fewer opioids, while benefiting from a positive hospital experience that is patient centered and age appropriate. There is a known small risk of motion sickness and nausea with the use of VR, but we believe that this risk will not be different in our study population, as evidenced by our previous VR study.

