## 3 INVESTIGATIONAL PLAN

#### 3.1 Study Design

This will be a randomized controlled pilot study comparing virtual reality to standard electronic use after pediatric idiopathic scoliosis surgery. Patients age 11-17 years old undergoing idiopathic scoliosis surgery will be included. Patients will be randomized to either the virtual reality or control (iPad) group. The randomization-and-concealment feature of REDCap data capture system will be utilized.

Subject eligibility will be verified by the research coordinator through chart review and patient questionnaire prior to enrollment in the study. The patients will be blinded to their study arm until they agree to be part of the study. Participants will be properly oriented to their respective device (VR or iPad) before surgery. While the use of VR may be new to the patients, VR is a very popular, trending and mainstream concept that is not likely to be unfamiliar to patients in the study age group. The patients will have the ability to stop using the VR device at any time if they choose.

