Both iPads and VR devices are interactive (regardless of fingers versus head movement) and this type of movement difference should not confound results. Our study aims to assess whether the VR immersive experience provides superior distraction to the standard of care (iPad use), thus by nature of the study design we are studying the difference in the two distinct types of experiences. Finger versus head movement use is inherent to the types of distraction and central to the distinct experiences. Similarly, there will be different apps between VR and iPad platforms by nature of the differences in platforms. Our goal is to examine whether an immersive experience is more beneficial than an iPad-based experience, rather than examine specific styles of games.

There will be no restriction to personal electronic use. Both groups will have access to their personal devices (cell phones, iPads) as is the standard of care. The study iPad will only be offered at specific times as designated twice a day on POD#1 for participants in the control group. Outside of the study windows, participants will not be provided with hospital iPads. Personal electronic devices including iPads are acceptable, as is the standard of care for patients to bring whatever they see fit into the hospital.

There will be a variety of popular games and apps, deemed to be content- and age-appropriate by the Child Life specialists. Program offerings will not vary by specific age or gender; our study will only include ages 11-17 and per discussion with Child Life the programs do not need to be subdivided to remain appropriate within this age range.

Standard of care for both groups will include PCA use as ordered by the surgical team as well as routine Child Life visits. The Child Life team is an integral part of pediatric postoperative recovery at UNC.

The following will be recorded: Number of hours since anesthesia end. Pain scores including FACES scale by the patient and FLACC scores by the research assistant will be recorded immediately prior to intervention (T=0) and at end of intervention (T=30); FLACC score will also be recorded at the 10 minute mark (T=10). PCA use, in mcg or mg as appropriate, for the hour prior to intervention (T=-60-0), during intervention (T=0-30), and one hour after intervention is complete (T=30-90) will be recorded. Total number of minutes of electronic device use will be recorded. PCA use will be converted to morphine equivalents at time of data entry.

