## **6.2** Secondary Outcomes

Our secondary outcomes and efficacy measures include: patient and caregiver satisfaction scores, presence of dizziness/nausea, time of discontinuation of VR/iPad if less than 30 minutes, and PHBQ-AS scores postoperatively at 48-72 hours and 7-10 days.

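### Nausea and dizziness have no stated pre-session reading, so existing symptoms cannot be told apart from those starting during device use, and the VR-iPad contrast is noisier than it need be.

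*Combined protocol and SAP*

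**What the plan says.** Section 5 lists the two items as "presence of dizziness (0=No, 1=Yes), presence of nausea (0=No, 1=Yes"). Section 6.2 makes them a secondary outcome: "presence of dizziness/nausea, time of discontinuation of VR/iPad if less than 30 minutes". Section 4.2 and the Synopsis list them too. None of these places gives a time of assessment, a reading before the session, an onset rule, a severity grade, or a rule for combining the morning and afternoon sessions.

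Other measures at the same visit do have a pre-session reading. For pain, section 3.1 says: "Pain scores including FACES scale by the patient and FLACC scores by the research assistant will be recorded immediately prior to intervention (T=0"). PCA use is taken "for the hour prior to intervention (T=-60-0), during intervention (T=0-30), and one hour after intervention is complete (T=30-90) will be recorded". Anti-nausea medication has a session window only: "Any anti-nausea medication requested during the intervention will be recorded" (section 4.5).

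On background symptoms, section 1.3 states: "Postoperative risks associated with children are related to opioid administration and include over-sedation, respiratory depression, nausea and vomiting". The Synopsis says: "Both groups of participants will also receive the postoperative standard of care including a PCA for pain control". Section 5.3 says that the incidence of dizziness and nausea with VR is not precisely known, and gives this as the reason for the 30-minute limit.

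**The concern.** On the protocol's own account, some patients can be expected to be nauseated from opioids on POD#1 before any device is offered. The recorded outcome is presence, not onset, so a patient who was nauseated beforehand and a patient made nauseated by the headset both score 1.

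Two things follow. First, the VR-arm proportion, which section 6.3 would tabulate with a confidence interval, mixes background with device-related symptoms and cannot serve as the tolerability rate that section 5.3 says is unknown. Second, the VR-iPad difference carries the sampling variation of background symptoms in both arms. A T=0 question would remove much of that variation. Once the sessions are over, T=0 status cannot be reliably recovered.

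**Working it through.** **The plan's own figure.** The sample size (20 completers, 10 per arm, at most 24 enrolled; sections 3.3 and 6.4) is a feasibility choice. No symptom rate, effect size or power is given, so there is nothing to reproduce.

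**Inputs.** From the documents: n = 10 per arm, two arms, PCA in both. Assumed, because the documents give no rates:
- background prevalence at T=0: b = 20-60%
- VR-induced onset among symptom-free patients: d = 10-30%
- spontaneous onset during a session: e = 5%

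**Step 1: chance imbalance before the session.** For two independent Bin(10, p) counts:

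| p | P(difference ≥ 2 patients) | P(difference ≥ 3 patients) |
|---|---|---|
| 20% | 0.394 | 0.157 |
| 30% | 0.463 | 0.220 |
| 40% | 0.494 | 0.253 |

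**Step 2: the VR-arm rate read alone.** The background share of VR-arm yes answers is b / [b + (1-b)d].
- b = 20%, d = 30%: 0.20/0.44 = 45%
- b = 40%, d = 20%: 0.40/0.52 = 77%
- b = 60%, d = 10%: 0.60/0.64 = 94%

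Over the assumed range, 45-94% of yes answers would be background.

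**Step 3: the arm difference, presence against new onset.**
- Presence: control b, VR b + (1-b)d, difference (1-b)d.
- New onset since T=0: control (1-b)e, VR (1-b)[1-(1-d)(1-e)], difference (1-b)d(1-e).
- Variance of each difference: [p1(1-p1) + p2(1-p2)]/10.

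The two outcomes target nearly the same difference. At b = 40%, d = 20%:
- Presence: 0.52 against 0.40, difference 0.12. Variance (0.2496 + 0.2400)/10 = 0.0490, SE 0.221, half-width 1.96 × 0.221 = 0.43.
- New onset: 0.144 against 0.030, difference 0.114. Variance (0.1233 + 0.0291)/10 = 0.0152, SE 0.123, half-width 0.24.
- Variance ratio: 0.0152/0.0490 = 0.31.

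Over b = 20-60% and d = 10-30%, the ratio runs from 0.16 (b = 60%, d = 10%) to 0.58 (b = 20%, d = 30%).

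**Step 4: sensitivity.** Step 3 leaves spontaneous onset out of the presence item. Putting it in gives 0.544 against 0.430 at b = 40%, d = 20%. The variance is then (0.2481 + 0.2451)/10 = 0.0493 and the ratio is still 0.31. At the two ends the ratios become 0.0742/0.4606 = 0.16 and 0.2346/0.4314 = 0.54, so the range barely moves. If background is only 10%, the Step 3 ratio is 0.64-0.78 and the gain is much smaller.

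**Step 5: what a T=0 reading does not achieve.** At b = 40%, d = 20%, two-sided 0.05 (assumed), Fisher power at 10 per arm is 2.6% for presence and 0.6% for new onset. About 270 and 95 per arm respectively would be needed for 80% power. Even 0 of 10 leaves a two-sided 95% upper bound of 31%.

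**The case against.** The strongest reply is that randomization already handles background. Section 3.1 says: "Patients will be randomized to either the virtual reality or control (iPad) group". Both arms have a PCA, and section 6.2 does not limit the symptom outcome to VR. A reader might infer from the missing baseline that opioid-related symptoms are counted as device effects. The documents do not support that: no section attributes a recorded symptom to the device, and the iPad arm subtracts background in expectation. With equal true rates of 20-60%, the exact Fisher false-positive rate is 0.8-1.3%, so there is no systematic inflation. This part of the objection stands. What remains is the rate within the VR arm, and precision.

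A second reply is that the imprecision comes mainly from 10 per arm, a declared pilot choice. That also stands: Step 5 shows the comparison is weak either way. But section 6.3 puts estimates and intervals first, and section 6.4 uses the pilot to try out procedures. A narrower interval and an interpretable onset rate serve both aims.

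Third, a reader might take these items as the only device-specific safety measure. They are not. The plan also records early discontinuation and minutes of use, logs anti-nausea requests during the session, has an assistant monitoring the patient (section 7) and reports adverse events (sections 6.5 and 9). None of these shows whether a patient was symptomatic at T=0.

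Finally, the documents do not say that each item is asked only once. They are silent on timing, and the codebook is still to be written (section 10).

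**Conclusion.** The point holds as a minor design improvement. As written, the plan cannot separate prior from new symptoms in an individual patient. The VR-arm rate is therefore not a device rate, and the arm difference, though not biased by background in expectation, is noisier than necessary. Under the assumed rates, a new-onset outcome has 16-58% of the variance of presence; in the central case the half-width is about 24 rather than 43 points. These sizes rest wholly on assumed symptom rates and shrink if background is low.

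It would go too far to call the comparison mostly noise because of the missing reading. That cannot be shown without symptom rates, and the small sample is a large part of the cause. The difference is also a net effect: if VR lowers PCA use, less opioid-related nausea could mask a device effect.

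**What to change.** Ask both arms about nausea and dizziness at T=0 and at T=30, or when the session stops early, in both POD#1 sessions. State in section 5 that the same question is put at the same times in the iPad arm. In sections 6.2 and 6.3, define the outcome as new onset since T=0. Report it by arm and session with exact confidence intervals, as a descriptive result alongside plain presence, and give a rule for combining the sessions. A symptom that starts in the morning and persists should count as a morning onset, not as afternoon background.

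Yes/no answers cannot show worsening in a patient who is already symptomatic. To capture that, add a simple severity grade or ask directly whether the symptom is worse than before the session.

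The cost is a few more data fields, since the research assistant is already at the bedside recording FACES at T=0 and T=30. The comparison stays imprecise at 10 per arm and should be reported as such.

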## 5.1 Efficacy Evaluation

During data analysis, number of hours since anesthesia end to start of visit will be extracted from chart review. PCA use conversion to morphine equivalents will be performed. Pain and anxiety scores and PCA opioid usage will be compared between the two study arms. These data will allow us to compare the two study arms and evaluate for efficacy.

#### 5.2 Pharmacokinetic Evaluation

Not applicable

## 5.3 Safety Evaluations

Safety and feasibility of VR in postsurgical populations has been proven in previous studies, some of which include specific spine surgery populations. As we are limiting the use of the virtual reality headset to 30 minutes, there is a possibility that patients may experience anxiety and/or notice an increase in pain following cessation of VR. As such, the patients will be permitted to freely use personal electronic devices without restriction, which is the standard of care at present. We feel that by doing this, the chance of anxiety related to complete withdrawal of electronic distraction will be low, as will

the possibility of any adverse effects such as nausea or dizziness. The incidence of dizziness and nausea with the use of virtual reality is not precisely known and is not agreed upon in the literature. As it is mentioned in various studies as a potential side effect, we will limit the use of the virtual reality headsets to 30 minutes to minimize the risk.

## **6 STATISTICAL CONSIDERATIONS**

#### 6.1 Primary Outcomes

Postoperative pain scores and postoperative PCA opioid usage surrounding intervention (in morphine equivalents).

## **6.2** Secondary Outcomes

Our secondary outcomes and efficacy measures include: patient and caregiver satisfaction scores, presence of dizziness/nausea, time of discontinuation of VR/iPad if less than 30 minutes, and PHBQ-AS scores postoperatively at 48-72 hours and 7-10 days.

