## Study phases are as follows:

Screening/Consent/Baseline: Randomization and consent will be obtained preoperatively. A baseline anxiety score will be assessed on a self-report form (STAI short form). Patients in the VR arm will be oriented to the VR device before surgery. All patients will be oriented to the Wong-Baker FACES pain scale. Baseline pain scores will be obtained through the following method: FACES scale (patient reported) and FLACC score (measured by the trained research assistant). Baseline vital signs will be measured and recorded. The STAI, FACES, and FLACC scoring tools have all been used and previously validated in the pediatric population.

Intervention/Treatment: On postoperative day (POD) #1 in the morning, patients in both groups will be visited by the research assistant. Standardized scripts will be utilized by the research assistant for the entirety of the data collection. Patients in the VR arm will be offered the VR device for up to 30 minutes. Patients in the control arm will be offered an iPad for up to 30 minutes. After a total of 30 minutes maximum, the session will end. Routine data will be collected on pain scores and PCA use as below for both groups. On POD #1 in the afternoon, a research assistant will return for patients in both

groups, for another session of the respective electronic device for up to 30 minutes. If a patient declines to participate, the reason for declining will be asked for and recorded.

In the control arm of the study, the iPad will have a variety of vetted and screened games available. The content on the iPads will include puzzles, games, and movies that have been previously vetted and approved by the Child Life team, separate from this study, and are currently used as standard of care at UNC. The Child Life team is an integral part of pediatric postoperative recovery at UNC.

In the VR arm of the study, there will be selected programs to choose from. All of the content will be pleasant games or exploring programs, avoiding unpleasant and fast-moving settings such as fighting or racing. All of the content will be age appropriate, vetted and screened by the research team for violence or otherwise stressing scenarios, content requiring rapid eye motion or head movement, and content requiring more body movement than what can comfortably be done in a sitting or reclined position.

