If a value is missing, the measure will be negated for that participant, and we will have an incomplete data point. These incomplete data points will not be included in the analyses. This study is based on prior work by our group with a quite rare occurrence of not being able to collect all data points, given the nature of the collected data. We do not anticipate that missing values will systematically introduce any selection bias.

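### The early-stopping outcome has a value only for patients who stop before 30 minutes, and the sections disagree on whether it covers both arms

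*Combined protocol and SAP*

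**What the plan says.** Section 6.2 includes "time of discontinuation of VR/iPad if less than 30 minutes" among the secondary outcomes and efficacy measures. Section 4.2 lists "Time of discontinuation of VR if less than 30 minutes", and the efficacy evaluations in the synopsis also name VR alone.

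Sessions are capped (section 3.1, study phases): "After a total of 30 minutes maximum, the session will end". Section 4.2 adds: "There will be two intervention/treatment visits, both occurring on POD#1". The same study-phases text says "Total number of minutes of electronic device use will be recorded", and the variable list in section 5 repeats this with no under-30 condition. Total minutes is not listed as an outcome in section 4.2 or 6.2, and neither is the proportion stopping early.

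Section 6.3 assigns the two-sample t-test to pain scores and opioid consumption. For other measures it promises tabulated estimates, proportions included, with confidence intervals. On absent values it says: "If a value is missing, the measure will be negated for that participant". Nothing states what value a completed or declined session receives, or how a patient's two sessions are combined.

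**The concern.** Whether a patient stops early is decided after randomisation and may depend on the device. The mean stopping time among stoppers therefore describes a different kind of patient in each arm. It also omits the most informative quantity, the number who stopped. A device that many patients put down at 20 minutes can look better than one that a single patient put down at 5.

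With 10 completed patients planned per arm there may also be too few stoppers to estimate a mean with a CI, although section 6.3 makes estimates and CIs the focus of the analysis. If the VR-only wording governs, nothing can be compared between arms at all.

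Section 6.4 says the pilot will also assess feasibility. How much of an offered session patients use bears directly on that, and this is the only listed outcome that measures it in minutes.

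**Working it through.** The documents give no stopping rate, expected difference or power for this outcome, so there is no stated figure to reproduce. Inputs from the documents: 10 completed patients per arm (section 3.3), a 30-minute cap, and two sessions per patient. All stopping rates and times below are assumptions.

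**1. Can the ranking reverse?** Take one session with 10 per arm. Four VR patients stop at 20 min, one iPad patient stops at 5 min, and the rest complete 30 min.

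| Summary | VR | iPad | Favours |
|---|---|---|---|
| Mean among stoppers | 20 | 5 | VR, by 15 min |
| Mean in all patients | (6×30 + 4×20)/10 = 26.0 | (9×30 + 1×5)/10 = 27.5 | iPad, by 1.5 min |
| Proportion stopping | 4/10 = 40% | 1/10 = 10% | iPad |

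So it can, with inputs chosen to show it.

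**2. Does it reverse in expectation?** Not necessarily. Suppose stopping times are exponential, with a proportion p stopping before 30 min, so λ = −ln(1−p)/30. The mean among stoppers is 1/λ − 30(1−p)/p, and the mean in all patients is p/λ.

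- p = 60%: 1/λ = 32.74. Stoppers: 32.74 − 20 = 12.74 min. All patients: 0.6×32.74 = 19.64 min.
- p = 10%: 1/λ = 284.74. Stoppers: 284.74 − 270 = 14.74 min. All patients: 0.1×284.74 = 28.47 min.

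The difference is 8.8 min in all patients and 2.0 min among stoppers. The sign is right, but most of the contrast is lost.

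This model was simulated with 10 per arm, one session and 200,000 replicates for each of eight pairs of rates (30–60% for the worse-tolerated device, 10–30% for the better). Where both arms had a stopper, the stoppers-only mean ranked the worse-tolerated device as better in 42–47% of trials. The all-patient mean did so in 1.5–20% of the same trials. In 3–37% of trials one arm had no stopper, so no stoppers-only comparison existed.

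**3. Is there enough to estimate?** With 0 or 1 stopper in an arm, no SD or CI for the mean time can be computed. For one session of 10 patients, P(at most 1 stopper) = (1−p)^10 + 10p(1−p)^9:

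- p = 10%: 0.349 + 0.387 = 0.736
- p = 20%: 0.107 + 0.268 = 0.376
- p = 40%: 0.006 + 0.040 = 0.046

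Pooling both sessions lowers these figures. If sessions were independent at 10% each, the chance of at most one early stop in 20 sessions is 0.122 + 0.270 = 39%. Counting patients instead, the chance of stopping in either session is 1 − 0.9² = 19%, so at most one such patient in 10 has probability 0.81^10 + 10×0.19×0.81^9 = 0.122 + 0.285 = 41%. If the same patients stopped both times, it stays at 74%.

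**4. Does the proportion avoid this problem?** Yes. Even with 0 of 10 stopping, an exact 95% interval exists: 0 to 1 − 0.025^(1/10) = 31%.

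**The case against.** The strongest reply is that the plan nowhere commits to comparing stopping times among stoppers. The t-test is reserved for pain and opioid use, and section 6.3 allows proportions. A table giving the number who stopped and when would satisfy section 6.2 without misleading anyone. That stands: a reader might infer that a stoppers-only comparison is planned, but the documents leave the analysis unspecified.

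A reader might also infer that completers are dropped under the missing-value rule. The text does not settle this. The rule concerns values that could not be collected and describes them as quite rare. A completed session has a recorded duration, so dropping completers is one possible application of the rule and not a stated one.

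A reader might further conclude that the tolerability result will come out reversed. The example in step 1 uses invented inputs and one session, and under the exponential model the expected difference keeps its sign.

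Nor does tolerability rest on this item alone. Dizziness/nausea is itself a secondary outcome, and anti-nausea requests, declines with reasons and a VR acceptance survey are also recorded.

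What the reply does not remove is the definition. The outcome as written gives completers no value, the sections disagree on its scope, and the proportion stopping is not listed.

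**Conclusion.** The point holds as a flaw in how a secondary outcome is defined, together with an inconsistency between sections 4.2 and 6.2 and the synopsis. Any between-arm summary of the times as written is conditional on an event after randomisation and leaves out the number of stoppers; under the VR-only wording no between-arm summary exists.

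Reversal is possible but not certain. Its size depends on assumed stopping patterns, because the documents give none. The sparse-data figures (74%, 38% and 5%) assume one session and independent patients, and fall if both sessions are pooled.

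Data collection and the primary outcomes are unaffected. The change is worth making because the outcome bears on feasibility and a better one can be built from minutes already recorded.

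**What to change.** Reconcile section 4.2, section 6.2 and the synopsis so that the outcome covers both arms, and replace it with two measures:

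- **(a) Minutes of study-device use per session**, from 0 to 30, with a completed session counted as 30 and a declined session as 0. Include all randomised patients who reach the POD#1 sessions. Report each session and the per-patient mean of the two. Give by arm the number of randomised patients who do not reach those sessions, since randomisation is preoperative and intensive care on POD#1 is an exclusion.
- **(b) The proportion in each arm stopping before 30 minutes**, with its CI. Show the number of declined sessions beside it, so that declining and stopping are not confused.

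The cost is wording only; the minutes are already recorded in both arms and no new data are needed.

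A separate, minor point: the section 5 variable list codes a decline as 0=Yes and 1=No, while dizziness, nausea and anti-nausea requests in the same list use 0=No and 1=Yes. A count of 1s would therefore give acceptances. Recode it as 0=No, 1=Yes when the codebook is built. This is one codebook line and carries no weight in the main point.
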